8.1.3. Unexpected Adverse Reaction

An unexpected AR is defined as an AR where the nature or severity of which is not consistent with the applicable product information (e.g., Investigator's Brochure for an unauthorized IMP or summary of product characteristics for an authorized product).

When the outcome of the AR is not consistent with the applicable product information this AR should be considered as unexpected.

8.1.4. Serious Adverse Event (SAE)

Any untoward medicinal occurrence or effect that at any dose:

- Results in death
- Is life-threatening
- Requires hospitalization or prolongation of existing hospitalization
- Results in persistent or significant disability or incapacity
- Is a congenital anomaly or birth defect
- Is another medically important event or reaction

Medical and scientific judgment should be exercised in deciding whether other situations should be considered serious such as important medical events that might not be immediately life-threatening or result in death or hospitalization but might jeopardize the participant or might require intervention to prevent one of the other outcomes listed in the definition above. Examples of such events are intensive treatment in an emergency room or at home for allergic bronchospasm, blood dyscrasias or convulsions that do not result in hospitalization, or development of drug dependency or drug abuse. Any suspected transmission via a medicinal product of an infectious agent is also considered a SAE.

Life-threatening in the definition of a SAE or serious AR refers to an event in which the participant was at risk of death at the time of event; it does not refer to an event that hypothetically might have caused death if it was more severe.

8.2. Reporting of Adverse Events

All study participants will be carefully monitored for the occurrence of AEs during the study period from the signing of informed consent to the completion of the last Follow-up Visit. The Investigator will collect AEs with a non-leading question such as “have you experienced any new health problems or worsening of existing conditions” as well as reporting events directly observed or spontaneously volunteered by participants.

A clinical laboratory abnormality should be documented as an AE if meet the following conditions: the test finding is accompanied by clinical symptoms AND/OR the abnormality suggests a disease and/or organ toxicity AND/OR the abnormality is of a degree that requires additional diagnostic evaluation(s) or medical/surgical intervention AND/OR the abnormality is considered clinically significant by the clinician.

Clearly related signs, symptoms and abnormal diagnostic procedure results should be grouped together and reported as a single diagnosis or syndrome whenever possible.

All AEs including but not limited to events reported by the participant, or reported in answer to an open question by the Investigator or member of this team, which fall into any of the above definitions must be recorded as an AE in the eCRF and should include the following information:

- Brief description of the event (diagnosis)
- Start date (and time, if relevant)
- Stop date (and time, if relevant) (or resolution)
- Severity
- Action taken regarding study drug
- Opinion on causality
- Seriousness (as defined in section 8.1.4 for definition of SAE, Serious Adverse Reaction (SAR) and Suspected Unexpected Serious Adverse Reaction [SUSAR])
- Outcome

8.2.1. Severity

Severity describes the intensity of an event, and will be assessed as:

- *Mild*: The AE does not interfere in a significant manner with the participant’s normal functioning level. It may be an annoyance.

- *Moderate:* The AE produces some impairment of function but not hazardous to health. It is uncomfortable and/or an embarrassment.
- *Severe:* The AE produces significant impairment of functioning or incapacitation and/or it is a hazard to the participant. An AE that is assessed as severe should not be confused with a SAE. Severe is a category utilized for rating the intensity of an event; and both AEs and SAEs can be assessed as severe.

If an AE changes in severity, the worst severity should be reported.

8.2.2. Causality

Causality will be assessed according to the WHO Causality Assessment as follows:

Related to IMP

- *Certain:* Event or laboratory test abnormality, with plausible time relationship to drug intake. Cannot be explained by disease or other drugs. Response to withdrawal plausible (pharmacologically, pathologically). Event definitive pharmacologically or phenomenological (i.e. an objective and specific medical disorder or a recognized pharmacological phenomenon). Re-challenge satisfactory, if necessary.
- *Probable/Likely:* Event or laboratory test abnormality, with reasonable time relationship to drug intake. Unlikely to be attributed to disease or other drugs. Response to withdrawal clinically reasonable. Rechallenge not required.
- *Possible:* Event or laboratory test abnormality, with reasonable time relationship to drug intake. Could also be explained by disease or other drugs. Information on drug withdrawal may be lacking or unclear.

Not related to IMP

- *Unlikely:* Event or laboratory test abnormality, with a time to drug intake that makes a relationship improbable (but not impossible). Disease or other drugs provide plausible explanations.

Conditional/Not classifiable

- Event or laboratory test abnormality. More data for proper assessment needed, or Additional data under examination.

Unassessable/Unclassifiable

- A report suggesting an AR that cannot be judged because information is insufficient or contradictory, and which cannot be supplemented or verified.

All AEs judged as having a reasonable suspected causal relationship to the IMP (i.e., possibly, probably, certain) as well as all AEs judged as unassessable/unclassifiable will be considered as related to IMP. Any AE that is considered to be related to the IMP is described as an AR.

8.2.3. Follow-up of Participants after Adverse Events

Any AE that is ongoing when after the End of Study Visit, should be followed up until the AE is resolved or the Investigator decides that the AE is stable and needs no further follow-up. For the last ongoing AE, any of these outcomes and the resolution date should be updated in the AE form in the eCRF.

8.2.4. Abnormal Laboratory Values/Vital Signs

Reporting of abnormalities as both laboratory/vital signs findings and AEs should be avoided.

A clinical laboratory abnormality should be documented as an AE if all the following conditions are met:

- The test finding is accompanied by clinical symptoms
- The abnormality suggests a disease and/or organ toxicity
- The abnormality is of a degree that requires additional diagnostic evaluation(s) or medical/surgical intervention.

If the laboratory test shows a relevant abnormality, it will be repeated to confirm it as soon as possible.

An asymptomatic abnormal vital sign finding should only be reported as an AE if it is clinically significant if it fulfils the criteria for an SAE or if it causes the participant to discontinue the study.

If an abnormal vital sign value is associated with clinical signs and symptoms, the sign/symptom should be reported as an AE and the associated vital sign result should be considered additional information.

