⁽¹⁾ All positive urine pregnancy test results must be confirmed by a serum hCG test

Study medication must be halted in all patients who fail to have platelet counts checked at the scheduled timepoints. The study medication should not be resumed until testing has been completed and confirmed to be within an acceptable range.

At the discretion of the PI, additional and repeat testing may be performed in scheduled visits as well as in unscheduled safety visits.

Clinically significant out-of-range values must be recorded as an adverse event on an AE Form or as a serious adverse event (SAE) on a SAE form, if applicable.

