8.4. Adverse Events of Special Interest

The following AEs (SOC and PT) or laboratory findings of special interest will be evaluated by PIs at all study visits and time points (as applicable):

- Investigations (SOC):
 - Platelet count decreased (PT)
 - Neutrophil count decrease (PT)

Platelet and neutrophils count decrease with minor hematological impact (i.e., at a given study visit, a decrease in the platelet or neutrophil count less than a 30% from baseline's count) are not to be reported as an AE unless, in the opinion of the investigator, the decrease is clinically significant.

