5.2.2 Adverse Events

Adverse events will be coded using the Medical Dictionary for Regulatory Activities (MedDRA) Version 23.1 or higher.

Treatment-emergent adverse events will be tabulated and are defined as those adverse events that either start or worsen in severity on or after the date/time of first dose of study treatment.

Where dates are missing or partially missing, adverse events will be assumed to be treatment-emergent, unless there is clear evidence (through comparison of partial dates) to suggest that the adverse event started prior to the first dose of study treatment.

For summary tables, AEs with “Certain”, “Probable/Likely” and “Possible” relationship to the study drug, as well as all AEs judged as unassessable/unclassifiable, will be considered related. In listings the more granular classification will be used.

The following AEs are considered to be of special interest:

- Investigations (SOC):
 - Platelet count decreased (PT)
 - Neutrophil count decrease (PT)

Only platelet and neutrophils count decrease with hematological impact (i.e., at a given study visit, a decrease in the platelet or neutrophil count *equal to or more than a 30% from baseline's count*) are to be reported as an AE unless, in the opinion of the investigator, the decrease is non-clinically significant.

An overall overview of TEAEs will be presented, including number of patients and frequency affected by different types of AEs as well as the number of events for each category by treatment:

- Any TEAEs
 - TEAEs related to study drug
 - TEAEs leading to study discontinuation
 - TEAEs by severity (mild, moderate severe)
 - TEAEs by outcome
- Any Serious TEAEs (STEAEs):
 - STEAEs related to study drug
 - STEAEs leading to study discontinuation
 - STEAEs by severity (mild, moderate severe)
 - STEAEs by outcome
- Any TEAEs of special interest
 - Platelet count decreased
 - Neutrophil count decreased
- Any COVID-19 TEAEs

The total number of subjects with at least one TEAE and the total number of TEAEs will be presented overall and by treatment arm and tabulated by MedDRA SOC and PT. In addition, AEs will be tabulated by worst severity and worst relationship to treatment.

The same tabulations will be provided for TEAEs, TEAEs of special interest, TEAEs leading to study drug discontinuation, serious TEAEs (STEAEs) and STEAEs related to study medication.

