5.2.4 Clinical Laboratory Evaluation

For summaries by visit, the last non-missing assessment (including repeat assessments) recorded at each visit will be summarized. Unscheduled and unplanned assessments will be listed, but not included in by-visit summaries.

For across visit summaries (e.g., maximum post-baseline value), scheduled, unscheduled and repeat assessments will be considered.

A subject will be defined as having a treatment-emergent laboratory abnormality if the subject had a normal baseline value and an abnormal post-treatment start value.

The following summaries will be provided for each laboratory category:

- A summary of each laboratory parameters (absolute values and change from baseline) by treatment and visit
- A summary of the number and percentage of patients experiencing treatment emergent laboratory abnormalities by parameter, visit (and overall, throughout the study)
- A shift from baseline table by visit

Laboratory values for hematology, serum biochemistry, serological parameters and urine parameters will each be listed by subject and study time point including changes from baseline (with the exception of serological and urine parameters). The baseline for the laboratory values will be the last results obtained prior to treatment (Day 1 according to schedule)

All values outside the clinical reference ranges will be flagged in the data listings. The abnormal values will be flagged with 'L' for values below the lower limit of the clinical reference range and 'H' for values above the upper limit of the clinical reference range and included in the listings. The Investigator will assess whether the values outside the clinical reference range are clinically significant. Clinically significant laboratory values will be recorded by the Investigator as AEs.

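### The rules for recording laboratory abnormalities as adverse events conflict, so the AE-based counts of platelet and neutrophil falls may be too low and may differ by site

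*Protocol*

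**What the plan says.** Three places in the protocol say when a laboratory abnormality becomes an adverse event.

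- Section 8.2 joins its conditions by AND/OR: "the test finding is accompanied by clinical symptoms AND/OR the abnormality suggests a disease and/or organ toxicity AND/OR" a need for further evaluation or intervention, with a fourth alternative that "the abnormality is considered clinically significant by the clinician".
- Section 8.2.4 says: "A clinical laboratory abnormality should be documented as an AE if all the following conditions are met". It lists symptoms, suspected disease or organ toxicity, and a need for evaluation or intervention. Clinical significance is not on its list. It also asks sites to avoid reporting the same abnormality both as a laboratory finding and as an AE.
- Section 7.3.5 says: "Clinically significant out-of-range values must be recorded as an adverse event on an AE Form".

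Platelet and neutrophil falls also have a specific rule, worded differently in the two documents.

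- Protocol 8.4: falls of less than 30% from baseline "are not to be reported as an AE unless, in the opinion of the investigator, the decrease is clinically significant". Nothing is stated for falls of 30% or more.
- SAP 5.2.2: only falls of 30% or more "are to be reported as an AE unless, in the opinion of the investigator, the decrease is non-clinically significant".

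SAP section 1 bars investigators from seeing the SAP before general unblinding. SAP 5.2.4 plans by-visit laboratory summaries with change from baseline, shift tables, listings and a count of treatment-emergent abnormalities. A participant enters that count "if the subject had a normal baseline value and an abnormal post-treatment start value".

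**The concern.** Protocol 5.2 names platelet and neutrophil depletion as the most relevant on-target tolerability effects, and they are the only two adverse events of special interest. A fall in a blood count is often found by the laboratory before the participant notices anything. If one recording rule requires symptoms and another does not, the same result can be an AE at one site and not at the next. The special-interest tables in SAP 5.2.2 are built from reported AEs, so they would carry that difference into the comparison of arms and into the AE summaries prepared for the DMC (SAP 5.2.11).

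**Working it through.** The plan gives no figure on this point, so there is none to reproduce. The check compares the rules, illustrates the possible loss, and then looks at what the laboratory outputs would still show.

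**1. Sections 8.2 and 8.2.4.** Let S = symptoms, O = disease or organ toxicity suspected, D = evaluation or intervention needed, C = clinically significant.

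- 8.2 records if S or O or D or C: 15 of the 16 combinations (all but none present).
- 8.2.4, read as a requirement, records if S and O and D: 2 of 16 (C present or absent).
- Every combination recorded under 8.2.4 is also recorded under 8.2, so they disagree in 15 − 2 = 13 of 16.
- Among the 8 combinations without symptoms, 8.2 records 7 and 8.2.4 records 0.

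**2. Asymptomatic platelet or neutrophil falls under each rule.**

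| Fall | 8.2 | 7.3.5 | 8.2.4 as a requirement | 8.4 | SAP 5.2.2 |
|---|---|---|---|---|---|
| 30% or more, out of range, clinically significant | AE | AE | no AE | not exempt; no instruction | AE |
| 30% or more, within range, clinically significant | AE | not covered | no AE | not exempt; no instruction | AE |
| 25%, out of range, clinically significant | AE | AE | no AE | AE | no AE |
| 30% or more, needs further evaluation, judged not clinically significant | AE | not covered | no AE | not exempt; no instruction | no AE |

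At 30% or more, 8.4 leaves the site to infer the answer or to go back to the general rules, which conflict. Below 30%, a clinically significant fall is an AE under 8.4 but not under the SAP wording.

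**3. Possible loss (illustration only).** Expected recorded events per arm = 94 × p × (1 − f × q). The 94 per arm is from Protocol 3.1. The rest are assumptions: p = true incidence of reportable falls, q = share without symptoms, f = share of participants at sites applying 8.2.4. With p = 10% and q = 90%:

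- f = 0: 94 × 0.10 = 9.4
- f = 25%: 9.4 × (1 − 0.225) = 7.3
- f = 50%: 9.4 × (1 − 0.45) = 5.2
- f = 100%: 9.4 × (1 − 0.90) = 0.9

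Over q = 50% to 100%, the loss runs from nothing (f = 0) to 50–100% of events (f = 100%). Strict use of 8.2.4 can only lower the count relative to 8.2.

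**4. What the laboratory outputs catch.** Change from baseline, shift tables and listings include everyone, whatever was reported as an AE. The treatment-emergent count has two gaps. Assume a platelet lower reference limit L of 140,000–150,000/mm³ (the documents give none).

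- Abnormal baseline: exclusion criterion 8j allows entry from 130,000/mm³. A participant whose last pre-treatment value lies between 130,000 and L cannot be counted.
- Falls within range: a 30% fall stays in range if baseline is at least L/0.7, about 200,000–214,000/mm³. A 50% fall stays in range if baseline is at least L/0.5 = 280,000–300,000/mm³.

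No planned output is specified as a count of participants by relative fall.

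**The case against.** The best defence is that 8.4 is the specific rule for these two events, has its own 30% threshold and no symptom condition, and would naturally be applied first. Section 7.3.5 separately compels recording of clinically significant out-of-range values, and SAP 5.2.4 agrees on clinical significance. Section 8.2.4 says to record if all conditions hold. It does not say only if, although it does use that restriction in its sentence on vital signs. The SAP wording cannot change what sites record, since they do not see it, and the SAP describes no step that removes a reported event.

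Much of this stands, and it limits the consequence. A reader might infer that the special-interest counts will be too low, or that an asymptomatic fall can never be recorded. Both inferences require sites to follow 8.2.4 over 8.2, 7.3.5 and 8.4, which the documents do not establish. A reader might also infer that the laboratory back-up drops everyone with an abnormal baseline, or that the question whether 1.2 mg lowers counts goes unanswered. Neither follows. The normal-baseline condition belongs to one summary in SAP 5.2.4. Change from baseline by arm and visit, and the shift tables (graded by clinical significance in Protocol 9.3.6), still address that question.

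The defence does not remove the conflict. Beside the instruction against double reporting, reading 8.2.4 as a requirement is natural, and 8.4 gives no explicit instruction at 30% or more.

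**Conclusion.** The recording rules contradict each other, and that rests on the text alone. The consequence is a risk: AE-based counts of platelet and neutrophil falls may be too low and may differ by site. Given strict use of 8.2.4 the direction is fixed, but the size cannot be derived, because it depends on how many sites apply that section and how many falls are without symptoms. The exposure is confined to AE-based tables. The laboratory outputs are a partial safeguard: they show falls, but do not count participants by relative fall, which is how the protocol itself describes this toxicity (below 30% in 1.6 and 8.4, at least 50% in 1.4.1 and 5.2). This should be corrected; it does not put the whole safety assessment in doubt.

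**What to change.** Reconcile Protocol 7.3.5, 8.2, 8.2.4 and 8.4 with SAP 5.2.2 into one recording rule that covers falls both below and at or above 30%. Which rule to adopt is for the sponsor to decide, and it must stand in the protocol, because sites cannot consult the SAP.

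Add one table on the Safety Analysis Set from central-laboratory data: number and percent of participants, by arm, by visit and at any time after baseline, whose platelet or neutrophil count fell by at least 30% and by at least 50% from baseline. Include participants regardless of baseline flag, put unscheduled values in the any-time row, and show the AE-reported counts beside it.

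The cost is wording changes in both documents and one more table from data already collected. The reported rate may look less favourable.

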8.3. Reporting of Serious Adverse Events

The Investigator is responsible for ensuring that all SAEs are reported to the Sponsor immediately, but in any event no later than 24 hours of any center personnel becoming aware of the event. Initial reports should be followed as soon as possible by detailed written reports. The initial and follow-up reports should identify participants by unique code numbers assigned in the study. The participants' names, personal identification numbers, and/or addresses must not be included. The following information is mandatory for the initial report:

- Participant study ID
- Study treatment (blinded, if applicable)
- Start date (time, if relevant) of the study treatment
- Brief description of the event (diagnosis)
- Start date (time, if relevant) of the event
- Seriousness criteria
- Causality assessment

For reported deaths, the Investigator should supply the Sponsor and the IEC (if applicable) with any additional requested information (e.g., autopsy reports and terminal medical reports).

SAE REPORTING CONTACT DETAILS

[REDACTED]

[REDACTED] [REDACTED]

[REDACTED]

[REDACTED] [REDACTED]

[REDACTED] [REDACTED]

SUSAR will be reported to CAs, IECs and PIs in accordance with EU legislation and local regulations. [REDACTED] will handle the submission of SUSARs.

8.4. Adverse Events of Special Interest

The following AEs (SOC and PT) or laboratory findings of special interest will be evaluated by PIs at all study visits and time points (as applicable):

- Investigations (SOC):
 - Platelet count decreased (PT)
 - Neutrophil count decrease (PT)

Platelet and neutrophils count decrease with minor hematological impact (i.e., at a given study visit, a decrease in the platelet or neutrophil count less than a 30% from baseline's count) are not to be reported as an AE unless, in the opinion of the investigator, the decrease is clinically significant.

8.5. Precautions/Overdose

Overdose should be reported as an adverse event. The definition of overdose is as follows:

1. Compliance >120% assessed by the Study Coordinator on visit days (considering the previous 2 weeks)
OR,
2. Daily compliance >200%, meaning if the participant takes 3 capsules or more within 24h

Administration of any dose that deviates from the scheduled regimen will be documented and reported by center personnel.

8.6. Pregnancy

Female participants will be instructed to notify the PI immediately if they become pregnant during the study. Male participants will be instructed to notify the PI immediately if their partner becomes pregnant. Pregnant participants will be withdrawn from further study treatment. The participants will also be instructed to report pregnancies discovered after the last visit, if they believe that conception occurred during their participation in the study.

A pregnancy as such is not an AE, unless there is a possibility that vafidemstat has interfered with the efficiency of any contraceptive measures. However, the Investigator should report pregnancies according to the procedures and timelines described for reporting of SAEs (Section 8.3). The pregnancy report form should be used instead of the SAE form.

The pregnant participant or partner will be followed until the end of the pregnancy. Any complication during the pregnancy should preferably be reported as an AE. The outcome of the pregnancy must be reported on the pregnancy report form. Any spontaneous abortion, stillbirth, birth defect/congenital anomaly, death, or other serious infant condition must be reported and followed up as an SAE.

